RESEARCH PROTOCOL

Date	7/20/20
Title	The influence of postoperative environment on patient satisfaction and perception of care following pelvic reconstructive surgery
Principal Investigator	[name]
Sub-Investigators	[name] MD MSc, [name] DO, [name] MD, [name] MD
Research Specialist	[name] MS,
Department	Department of OB/Gyn, Division of Urogynecology and Reconstructive Pelvic Surgery
Hatton #	17-076
NCT #	03379753

Purpose of Study

- To determine the influence of homeopathic therapies such as music therapy and images of calming nature scenes in their hospital suite following vaginal reconstructive surgery for pelvic organ prolapse on parameters of recovery such as pain, satisfaction and perception of care.
 - **Primary Aim:** To determine if patients following prolapse repair including vaginal vault suspension have decreased pain measured via a visual analog scale (VAS) on postoperative day one and just prior to discharge when exposed to the diad of music, and positive images compared to patients receiving standard care.
 - **Secondary Aims:** To determine if patients following prolapse repair including vaginal vault suspension have improved satisfaction scores and perception of care when exposed to the diad of music, and positive images compared to patients receiving standard care.

Hypothesis or Research Question

- We hypothesize that patients exposed to alternative therapies such as music, and calming nature scenes will have decreased VAS scores for pain following vaginal reconstructive surgery when compared to controls.
- We further hypothesize that patients who experience the modified post-operative environment will report an improvement in overall satisfaction when providing their

overall hospital rating and will be more likely to refer their friends to the hospital for care in the future, as measured by the HCAHPS and VAS satisfaction scores.

Background

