 - VAS pain scores prior to discharge based on the validated SPS pain questions²⁵.
 - VAS for satisfaction with their hospital stay prior to discharge
 - Nursing recording pain scores prior to delivery of pain medications (recorded in Epic)
 - Total morphine equivalents during hospital stay

- Patient reported impression of the music and art using Likert scales, at discharge and 2 weeks post operatively for the intervention group
- Patient impression of the hospital based on responses from modified HCAHPS questions prior to discharge on post-operative day one:
 - First Question in VAS format: “Compared to other hospitals, how would you rate this hospital”?
 - Second Question in VAS format: “How likely are you to recommend this hospital to family and friends?”
- Patient VAS scores concerning their perception of the healing environment of the hospital and whether they would choose the hospital again
- Responses at the 2 week postoperative appointment to another identical series of VAS for satisfaction and pain, questions 21 and 22 from the HCAHPS survey, a question on pelvic symptoms after surgery, and the validated Decision Regret Scale for pelvic floor disorders²⁴
- General Demographic Data
 - Age, BMI, race, history of depression, home medications, sexual activity, alcohol use, prolapse stage, procedures performed, voiding trial results, length of stay, surgical and postoperative complications, and estimated blood loss
- *VAS Score Validity:*
 - The VAS score is a well-established tool for measuring a patient’s pain level that has been in clinical practice for decades. This tool has been applied throughout the medical field as a standardized measure of pain and remains a common method of characterizing pain levels by researchers. It has been shown to be reliable in the assessment of acute pain¹⁸.
- *HCAHPS survey questions:*
 - Survey is the first national, standardized, publicly reported survey of patients' perspectives of hospital care. HCAHPS (pronounced “H-caps”),

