also known as the CAHPS® Hospital Survey, is a 32- item survey instrument and data collection methodology for measuring patients' perceptions of their hospital experience. Beginning in 2002, CMS partnered with the Agency for Healthcare Research and Quality (AHRQ), another agency in the federal Department of Health and Human Services, to develop and test the HCAHPS Survey. AHRQ and its CAHPS Consortium carried out a rigorous and multi-faceted scientific process, including a public call for measures; literature review; cognitive interviews; consumer focus groups; stakeholder input; a three-state pilot test; extensive psychometric analyses; consumer testing; and numerous small-scale field tests. CMS provided three opportunities for the public to comment on HCAHPS and responded to over a thousand comments. The survey, its methodology and the results it produces are in the public domain¹⁹.

- HCAHPS question 21: "Using any number from 0-10, where 0 is the worst hospital possible, and 10 is the best hospital possible, what number would you use to rate this hospital during your stay?"
- HCAPS question 22: "Would you recommend this hospital to your friends and family?"
 - Definitely No
 - Probably no
 - Probably yes
 - Definitely yes

- Data Collection tool
- **Intervention or experimental aspect of the study**
 - Music
 - The patients will have access to a blue tooth capable audio device in their hospital rooms that can connect to their own device or one that will be provided for them. Selections of music and relaxation sounds will be

available and they will be shown how to use the device during post-operative rounds.

- Music selections will generally maintain a relaxing tempo of 60-80bpm.
- Subjects will have no limit to the amount of music they can listen to, however they will be asked to spend 30 minutes upon arrival to their room, when getting up to the chair for the first time, and following their voiding trial. At a minimum, the audio device will be turned on for the patient during post-operative rounds, and during morning rounds if they have not yet done so.

- Landscape

- Patients will have a large print of a soothing nature landscape hung on the wall near the foot of their bed. The size will approximate 24x36 inches. Each subject will have one scene in their room.
- The scenes will be hung to the wall with a removable hanger.
- Scenes were selected based on the preferences of individual surveys carried out with 86 volunteers.

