- **Statistical Analysis**

- Descriptive statistics will be calculated for all continuous and categorical data. Continuous variables will be summarized as mean (SD) or median (range). Categorical variables will be presented as frequency (Percentage). The primary outcome is the VAS scores for pain in the morning of post-op Day 1 (POD 1). Student's t-test or Mann-Whitney U test (Wilcoxon Rank Sum test) will be implemented to test for significant difference in pain and satisfaction scores and narcotic use between intervention and control groups. Assumptions will be examined and appropriate parametric or non-parametric tests will be used. For categorical data, Chi-square or Fisher's exact test will be employed to test the association.

Ethical Considerations

- **Informed consent**

- Patients who agree to participate in the study will sign a written informed consent. They will be consented by one of the stated investigators or trained Research Nurse and they will receive a copy of the signed informed consent statements (ICS). A copy will be put in their medical file.
- **Privacy information**
 - Extensive efforts will be made to ensure participant confidentiality and prevent unauthorized release of personal information. Electronic study documents will be stored on a secure drive and hard copy documents stored in a locked area. Thereby, all identifying and protected health information, including name and date of birth, will be maintained in a secure area at all times, accessible by authorized personnel only.
 - All communication between staff members regarding participant data will occur via the Subject ID number only. However, identifying information will be retained in the original/source documents.
 - The participant will be logged in the Excel spreadsheet and assigned a Subject ID number. Each participant will be assigned the next available Subject ID number. Once each Subject ID number has been assigned, it will not be reassigned.
 - Study documentation, both electronic and hard copy will be stored securely for ten years and then destroyed.
- **When and how will results be disseminated?**
 - We plan for the results to be disseminated in Spring 2020 at a national meeting in the form of a poster or oral presentation. We also plan for the results to be published.

References

1. Nightingale, F. Sick nursing and health nursing. Summary. Chicago: The International Congress of Charities, Correction and Philanthropy. 1893.

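### Does the plan lose power on the four-answer recommendation question (HCAHPS question 22) by not saying which test applies to it?

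*Combined protocol and SAP*

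**What the plan says.** All references are to the combined protocol and SAP.

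- **The outcome.** Under Data Collection, Secondary Outcomes, the 2-week assessments include "questions 21 and 22 from the HCAHPS survey". The text on the HCAHPS survey gives question 22 as "Would you recommend this hospital to your friends and family", with four verbal answers running from a definite no to a definite yes.
- **The hypothesis.** Under Hypothesis or Research Question, intervention patients "will be more likely to refer their friends to the hospital for care in the future", and this is to be judged "as measured by the HCAHPS and VAS satisfaction scores".
- **The score rule.** Under Statistical Analysis, the t-test or Mann-Whitney test is used "to test for significant difference in pain and satisfaction scores and narcotic use between intervention and control groups". The section adds: "Assumptions will be examined and appropriate parametric or non-parametric tests will be used".
- **The categorical rule.** The same section ends: "For categorical data, Chi-square or Fisher's exact test will be employed to test the association".
- **A companion item.** Before discharge the same idea is measured on a visual analogue scale: "How likely are you to recommend this hospital to family and friends".

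No section assigns question 22 to either rule by name.

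**The concern.** Four verbal answers look like categorical data, so an analyst could reasonably build a 2x4 table and apply Chi-square or Fisher's exact test. Both give the same p-value however the four columns are arranged, so neither uses the order. The hypothesis has a direction: intervention patients should recommend the hospital more. A rank test puts all its sensitivity into that direction, whereas the 2x4 test spreads it over three degrees of freedom. If the intervention moves answers upward along the whole scale, the unordered test is more likely to miss it. The choice between tests of different power is also left open until the data are in hand.

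**Working it through.** **1. Inputs from the plan.** The documents give no sample size, answer pattern, target effect or alpha for question 22. The only planned size is for the primary pain outcome: difference 1 cm, SD 1.4, power 90%. With two-sided alpha 0.05 (assumed, because none is stated), n = 2(1.960 + 1.282)² × 1.4² = 41.2, so 42 per arm. Solving with the t distribution gives 42.2, so 43, which is the plan's figure. A one-sided 0.05 gives 34 and does not match. The revised total of 132 with 20% loss leaves 132/2 × 0.80 = 52.8 per arm. Question 22 is therefore examined at 43 and at 52 or 53 per arm.

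**2. Assumed answers.** The share giving the top answer in controls is set at 40, 60, 75 or 85%. The rest is split 10/20/70, 5/10/85 or 20/30/50 over the three lower answers. The effect is a proportional-odds shift.

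**3. One case by hand.** Take 40% top answers and the 10/20/70 split, so controls are 6/12/42/40%. An odds ratio of 2 halves each cumulative odds:
- 0.06/0.94 ÷ 2 = 0.0319, a proportion of 0.031
- 0.18/0.82 ÷ 2 = 0.110, a proportion of 0.099
- 0.60/0.40 ÷ 2 = 0.75, a proportion of 0.429

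The intervention arm is then 3.1/6.8/33.0/57.1%.

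- *Unordered test.* The noncentrality is 2n Σ(half-difference)²/(mean proportion) = 86 × 0.0324 = 2.8. On 3 degrees of freedom (critical value 7.81) this gives about 26% power.
- *Mann-Whitney.* The chance that an intervention patient answers higher, plus half the chance of a tie, is 0.406 + 0.189 = 0.595. The tie-corrected z is about 1.66, which gives about 38% power.

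Simulation, using exact Fisher when an expected count is below 5 and Chi-square otherwise, gives 37.5% for Mann-Whitney and 26.4% for the categorical rule.

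**4. Simulated power over the range (10,000 trials per scenario).**

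| Case (10/20/70 split, 43 per arm, OR 2) | Mann-Whitney | Categorical rule, 2x4 |
|---|---|---|
| 40% top answer | 37.5% | 26.4% |
| 85% top answer | 17.7% | 11.0% |

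Over all the assumed patterns the categorical rule loses 2.5 to 7 points at OR 1.5, 5 to 15 at OR 2 and 8 to 17 at OR 3. Part of this is Fisher's conservatism rather than the lost order: at 85%, OR 3, 43 per arm, the loss of 11.9 points falls to 6.5 with mid-p Fisher.

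**5. Other one-directional shifts.** Suppose only the second-lowest answer moves up one step: controls 4/16/20/60%, intervention 4/2/34/60%. No cumulative proportion worsens.
- *Unordered test.* The noncentrality is 86 × (0.07²/0.09 + 0.07²/0.27) = 6.2.
- *Mann-Whitney.* The probability measure is only 0.309 + 0.216 = 0.525.

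Simulated power at 43 per arm is about 60% for the categorical rule and 7 to 8% for Mann-Whitney. With 5/15/40/40% against 5/2/53/40% it is 48% against 10%. Direction alone does not make the rank test the stronger one; the result depends on the shape of the shift.

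**6. Other readings the plan permits.**
- *Collapse to the top answer against the rest.* The gap to Mann-Whitney is −2 to 5 points at 40 to 75% top answers and 0 to 8 at 85%. The gap at 85% comes largely from switching to Fisher: at OR 3, 43 per arm, plain Chi-square on the 2x2 table gives 33% against 32% for Mann-Whitney, and Fisher gives 24%.
- *t-test on codes 1 to 4.* It is 0 to 6 points below Mann-Whitney.

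**7. Type I error.** In the null runs Mann-Whitney stays at 4.8 to 5.4%. The Chi-square/Fisher rule stays at 3.8 to 5.4%, and plain Chi-square on very sparse tables drops to 2.7%.

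**The case for a change.** The strongest case for a change is that it would be free. Mann-Whitney is already in the section, the hypothesis is directional, and one sentence would fix both the test and the handling of the levels. There is also a cost beyond power. If someone computed both tests and reported the smaller p-value, the false-positive rate would rise to 6.4 to 8.1%, or 6.7 to 9.7% with the collapsed table as a third option. The pre-discharge item does not close the gap, because it uses a different response scale at a different time.

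The silence is real, and so is the loss under proportional odds. The inflated error rate is a worst case. It needs selection by p-value, which nothing in the plan permits or suggests, and it would touch one secondary item. The power argument holds only for the assumed model, as step 5 shows. A sentence naming the test would make the plan tidier but would correct nothing in it.

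**Conclusion.** This is a gap that analysts fill sensibly, and no change to the plan is needed. The hypothesis groups HCAHPS with the satisfaction scores, and the analysis section assigns satisfaction scores to the t-test or Mann-Whitney and calls for whichever is appropriate. A statistician faced with four ordered answers can use the rank test under the text as it stands. A top-answer comparison is also permitted and usually costs little. The loss arises only if the analyst chooses the categorical rule, keeps all four columns, and the true effect is close to a proportional-odds shift. It is then about 5 to 15 points at an odds ratio of 2 and 8 to 17 at 3, at 43 to 52 per arm and two-sided 0.05. These figures rest wholly on assumed answer patterns, because the documents give none. At an odds ratio of 2, Mann-Whitney itself reaches only about 17 to 47% under those patterns, so a moderate shift would usually be missed by either test. No permitted test is invalid, and no stated figure or primary conclusion changes.
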